9.8 Analysis of Other Services Used

Weekly days of attendance at self-help meetings or other professional service providers to help reduce/quit drinking at study week 13 will be presented as summary statistics by treatment group. All other services used data will be presented in the listings.

9.9 Concomitant Medications, Medical History, and Pregnancy Tests

Concomitant and prior medications are collected at screening and at all study weeks and will be presented in a subject listing, as will pregnancy tests. Medical History will be coded using MedDRA, summarized in a table by treatment group and will be presented in subject listings. No statistical inference will be performed.

9.10 Eligibility and Screen Failures

Screen failures will be summarized in a table and provided in subject listings. Answers to eligibility criteria will be provided in the subject listings.

9.11 Exploratory Analyses

A number of variables will be tested as potential moderators of the medication treatment effect on the PHDD primary endpoint. Weeks 3-12 will be the period of interest. The model identified in Section 9.4.1 will be amended to include the potential moderator variable and the moderator by treatment group interaction. To aid with interpretation, continuous moderator variables will be dichotomized based on clinically accepted levels available from the literature. In the event a clinically meaningful cutoff is not available, LOESS curves will be used to identify a cut point. The LOESS curve analysis will use averaged PHDD data over study weeks 3-12, treatment group and the moderator of interest. In all approaches, an appropriate cutoff will be one that ensures a sufficient sample size in all resultant subgroups. The potential moderator variables are assessed at baseline and include: sex, IDS-30 reward/relief drinking, baseline drinks per week, measures of anxiety and depression (ECR-RS anxiety-related attachment, POMS subscales of depression and anxiety, Spielberger Trait Anxiety Inventory), Barratt Impulsiveness Scale, history of alcohol withdrawal (i.e., withdrawal question on the MINI for alcohol use disorder), and alcohol-related treatment goal.

There is interest in exploring the use of a new Hyperkatifeia Scale as an efficacy endpoint and moderator of drug response. Hyperkatifeia scores are assessed at Week 1 and Week 13 (EOS Visit 9). Exploratory analyses utilizing Hyperkatifeia Scale scores will include: 1) using the total score and subscales as an endpoints to assess treatment efficacy; and 2) conducting moderator analyses using total score and the subscales. The total score and subscales are the sum of the items.

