attachment anxiety, such that oxytocin reduced craving in more anxiously attached individuals and increased craving in less anxiously attached individuals. Subjects did not display an approach bias to alcohol images on the placebo day, preventing meaningful analysis of the effects of oxytocin on this measure. However, subjects did display an approach bias to appetitive images on the placebo day, which was significantly reduced by oxytocin administration. No adverse reactions were reported.

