## 11.4.7. Exploratory Analyses

A number of variables will be tested as potential moderators of the medication treatment effect on the PHDD primary endpoint. Weeks 3-12 will be the period of interest. Continuous moderator variables will be dichotomized. The potential moderator variables that will be examined include measures of anxiety and depression (ECR-RS subscales of attachment and anxiety, POMS subscales of depression and anxiety, STAI, and BIS), those suggestive of alcohol withdrawal (i.e., withdrawal question on the MINI for alcohol use disorder), and alcohol-related treatment goal.

There is interest in exploring the use of a new Hyperkatifeia Scale as a predictor and moderator of drug response. Exploratory analyses utilizing Hyperkatifeia Scale scores will include:

1) conducting moderator analyses using the total score; and 2) comparison of change from baseline between treatment groups for total score and subscales scores.

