7.0 SAMPLE SIZE CONSIDERATIONS

With an intake sample of 100 subjects (50 subjects per arm) and 12% attrition, it is projected that the sample size for primary endpoint analyses will be 88 (44 subjects per arm). The alpha level for the primary analyses will be 0.05, two-tailed. An estimate of the effect size (Cohen's d) for the investigational products is 0.60. Equal variances in both groups are assumed. These assumptions lead to a projected power of 0.80.

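### Every continuous moderator is split in two before its treatment interaction is tested; if the moderator is near-normal and the interaction linear, that discards about 36-51% of the information on the interaction

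*SAP*

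**What the plan says.** SAP section 9.11 takes the primary mixed model of section 9.4.1, which "will be amended to include the potential moderator variable and the moderator by treatment group interaction". It then says, giving interpretation as the reason, that "continuous moderator variables will be dichotomized based on clinically accepted levels available from the literature". Cutoffs come from the literature where they exist. Otherwise: "In the event a clinically meaningful cutoff is not available, LOESS curves will be used to identify a cut point". The only constraint on where the cut falls is that "an appropriate cutoff will be one that ensures a sufficient sample size in all resultant subgroups"; no proportion is given. Protocol section 11.4.7 is shorter and unqualified: "Continuous moderator variables will be dichotomized".

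The shells agree with that reading. SAP Table 117 has one treatment-by-moderator term on 1 degree of freedom and least squares means for a Yes/No split, and Tables 118 to 125 follow its style. No continuous-scale interaction test appears in either document.

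The moderators affected are attachment anxiety (ECR-RS), POMS depression and anxiety, trait anxiety (STAI), Barratt impulsiveness, IDS-30 reward and relief scores, baseline drinks per week and, by the format of Table 125, Hyperkatifeia. Sex, the MINI withdrawal item and drinking goal are binary by nature and are not affected.

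**The concern.** A split treats everyone on one side of the cut as identical and separates people who sit just either side of it. Where the treatment effect changes smoothly along the scale, that throws away information, whatever the source of the cut. A literature cutoff is protected from data-driven selection but not from this loss, which depends on where the cut falls in the trial's own sample.

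The trial is sized for the overall treatment effect only, and no power is stated for any moderator. Interaction tests are weak at this size to begin with, and a further loss makes it more likely that a real moderator is missed. Nothing is gained in error control. Finding out who responds is a declared interest of the plan. One of its moderators has prior support: Protocol section 4.1.6 reports that after a single dose "oxytocin reduced craving in more anxiously attached individuals and increased craving in less anxiously attached individuals". A cut placed away from the crossover would mix opposite effects within one group.

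**Working it through.** **Inputs from the documents.** SAP section 7.0: "With an intake sample of 100 subjects (50 subjects per arm) and 12% attrition", leaving 88 analysed (44 per arm); overall d = 0.60; two-sided alpha 0.05; projected power 0.80.

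**The plan's own figure.** 100 × (1 − 0.12) = 88. Normal approximation: 0.60 × √(44/2) = 2.814; 2.814 − 1.960 = 0.854; power = 0.804 (0.795 by noncentral t). The stated 0.80 is reproduced. It concerns the primary comparison only.

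**Information kept by a split.** Assume a normal moderator and a linear interaction. Cutting so that a proportion q lies on one side keeps a fraction φ(z_q)² / [q(1 − q)] of the information on the interaction slope.

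| Split | Calculation | Kept | Lost | 88 subjects act like |
|---|---|---|---|---|
| 50/50 | 0.3989² / 0.25 | 0.637 | 36% | 56 |
| 30/70 | 0.3477² / 0.21 | 0.576 | 42% | 51 |
| 20/80 | 0.2800² / 0.16 | 0.490 | 51% | 43 |

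The percentages do not depend on the sample size.

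**Power, analytically.** Take an interaction with 80% power on the continuous scale, so a noncentrality of 1.960 + 0.842 = 2.802. After the split, power is Φ(2.802 × √kept − 1.960): 61%, 57% and 50% for the three splits.

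**Power, by simulation.** Set-up: N = 88, 1:1, normal moderator, residual SD 1, fixed cut, two-sided 0.05, one outcome per subject and ordinary least squares in place of the repeated-measures model. The slopes, in SD of outcome per SD of moderator, are assumptions.

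| Assumed slope | Continuous | 50/50 | 30/70 | 20/80 |
|---|---|---|---|---|
| 0.6, moderator not prognostic | about 77% | 57% | 53% | 46% |
| 0.6, moderator also prognostic (0.3 SD per SD) | 76-77% | 53% | 47% | 39% |
| 0.4, moderator not prognostic | about 44% | 32% | 28% | 24% |

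A separate run at essentially the first slope (2.802 × 2/√88 = 0.597) gave 58%, 52% and 43%, so these figures are good to about three points. With no interaction, both tests reject about 5% of the time.

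**Changing the assumptions.**
- Uniform moderator: the loss is 25% at the median, 37% at 30/70 and 52% at 20/80.
- Right-skewed moderators (lognormal, gamma): about 36-73%, depending on which tail is cut.
- True step exactly at the cutoff: the order reverses, with simulated power of 76-79% for the split and 45-57% for the continuous term.

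**The case against.** The case for leaving the plan alone has real content.

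- **The loss is conditional.** A reader might infer that the plan discards 36-51% of the information outright. The documents give no moderator distribution and no interaction shape, so that reading is not supported. A clinically accepted cutoff is also the place where a step is most plausible, and there the split is the better model. This stands, and it is why the claim is conditional.
- **The worst case may not arise.** A 20/80 split puts about 0.2 × 44 ≈ 9 subjects per arm in the smaller group, which the sufficient-size rule might exclude. That rule names no threshold, however, and a 50/50 split already loses 36% under the stated assumptions.
- **The 0.6 slope is large.** It moves the treatment effect by 1.2 SD between one SD below and one SD above the moderator mean, twice the planned overall d of 0.60. At 0.4 the continuous test reaches only about 44%. The change improves a screen that remains weak.
- **The attachment-anxiety evidence is limited.** A reader might take Protocol section 4.1.6 as showing a graded effect along the scale. It supports a reversal between more and less anxious people, for single-dose craving in people not seeking treatment. It does not establish a gradient, and a two-group test can also detect a reversal.
- **The analyses are exploratory.** Protocol section 11.4.11 calls the trial a pilot, and nothing here touches the primary test. This stands and limits the weight of the point.

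One defence does not stand: that splitting for interpretation means display only. No continuous test is specified, and Table 117 tests the split.

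**Conclusion.** The point holds in conditional form. Both documents dichotomize every continuous moderator before the interaction test and plan no test on the continuous scale. For a roughly normal moderator with a roughly linear interaction, the loss is about 36% at a 50/50 split, rising to 51% at 20/80. At an assumed slope of 0.6 and 88 analysed subjects, that costs roughly 20 to 31 percentage points of power, and slightly more if the moderator is also prognostic. At 0.4 it costs 12 to 20 points. There is no gain in type I error.

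Normality, linearity and the slopes are assumptions. The 88 is the projected sample after attrition from 100 randomized; because the primary analysis uses the available data in the Full Analysis Set, the effective number may lie between the two. A reader should not conclude that splitting is always inferior, or that the trial's main conclusion is at risk; the documents support neither. This is a cheap improvement to an exploratory analysis.

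**What to change.** In SAP section 9.11 and Protocol section 11.4.7:

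1. Make the treatment by continuous-moderator term, added to the section 9.4.1 model, the moderator test, and report its p-value.
2. Prespecify a linearity check, by a quadratic term or a spline, for every continuous moderator. LOESS is currently planned only where no literature cutoff exists, so it does not cover the rest.
3. Report the treatment effect with its 95% confidence interval at the 25th, 50th and 75th percentiles of the moderator.
4. Keep the two-group least squares means at the literature cutoff as a display, without a separate interaction test.

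The cost is revised wording in two sections and several added rows in the shells for the continuous moderators among Tables 117 to 125. No new data and no different base model are needed. The downside is that a functional form is assumed: a linear term can miss a threshold or a U-shape, which is why the check in step 2 belongs in the plan.

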5.7 Hyperkatifeia

Hyperkatifeia is defined as a greater intensity of negative emotional/motivational signs and symptoms during withdrawal from drugs of abuse in the withdrawal/negative affect stage of the addiction cycle (Koob 2021). Hyperkatifeia or negative emotional state is considered to be one of stages of addiction in the context of drug withdrawal (Koob and Le Moal 1997, Koob 2019). NIAAA has developed a 24-item self-report Hyperkatifeia Scale to capture negative emotionality after stopping alcohol drinking that will be assessed for the first time in this study of heavy drinkers with a diagnosis of moderate to severe AUD. The items address four measures associated with negative emotional state including anxiety, depression, stress, irritability and pain. Each item is is 5-point Likert scale assessing the intensity of the feelings and sensations experienced when not drinking alcohol. Higher scores are indicative of greater intensity of hyperkatifeia.

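### Where no literature cutoff exists, SAP 9.11 picks the moderator cut from LOESS curves of the primary outcome using treatment group, and the table shells report uncorrected p-values at that cut on the same data

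*SAP*

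**What the plan says.** SAP 9.11 tests baseline variables as moderators of the treatment effect on weekly percentage of heavy drinking days (PHDD), weeks 3-12. On the model: "The model identified in Section 9.4.1 will be amended to include the potential moderator variable and the moderator by treatment group interaction". On the form of the moderator: "To aid with interpretation, continuous moderator variables will be dichotomized based on clinically accepted levels available from the literature". On the fallback when there is no such level: "In the event a clinically meaningful cutoff is not available, LOESS curves will be used to identify a cut point". The inputs to LOESS are these: "The LOESS curve analysis will use averaged PHDD data over study weeks 3-12, treatment group and the moderator of interest". Any cut must also leave enough subjects in every subgroup, but no number is attached.

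Protocol 11.4.7 is shorter: "Continuous moderator variables will be dichotomized". It gives no method.

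The fallback will be needed for at least one scale. SAP 5.7 says the Hyperkatifeia Scale "will be assessed for the first time in this study of heavy drinkers", and neither document gives a cutoff for it. SAP 9.11 plans "conducting moderator analyses using total score and the subscales".

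The Hyperkatifeia moderator shell, SAP Table 125, follows the style of Table 117. That shell has a p-value for the arm-by-moderator term, and a p-value and Cohen's d for oxytocin versus placebo within each split. Neither document mentions a LOESS span, a rule for reading a cut from the curves, separate data, resampling or a correction.

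**The concern.** A cut chosen by looking at how the arms differ along the moderator, and then tested in the same subjects, outcome and weeks, has been partly fitted to noise. Its p-values can be too small, and the two subgroup effects can look further apart than they are. Elsewhere the SAP is more careful: in 9.4.3, extra covariates are chosen before unblinding, from correlations pooled across arms. The moderator cut has no such safeguard.

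Hyperkatifeia as a moderator of drug response is a stated interest of the trial. A threshold reported for a new scale is the kind of result a later study may adopt as an entry or stratification rule.

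**Working it through.** **Inputs from the documents.** 88 subjects analysed, 44 per arm; d = 0.60; two-sided alpha 0.05 (SAP 7.0, 9.1). Baseline PHDD and clinical site are in the model (SAP 9.4.1), and there are 4 sites (SAP 3.2).

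**The plan's own figure.** No error rate or power is given for the moderator analyses. The stated primary power of 0.80 reproduces: 0.60 × √(44/2) = 2.814; 2.814 − 1.960 = 0.854; Φ(0.854) = 0.804. The noncentral t with 86 df gives 0.795.

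**Assumptions.** In the main runs the moderator is unrelated to outcome. Baseline PHDD correlates 0.3, 0.5 or 0.7 with averaged PHDD. The treatment effect is 0 or −0.6 SD. The outcome is normal or bounded 0-100. Each arm has its own local-linear LOESS curve, span 0.5 or 0.75. Cuts are kept between the 25th and 75th percentiles, so each subgroup has at least 0.25 × 88 = 22 subjects. There were 19 settings of 4000 runs each; the Monte Carlo standard error at 5% is √(0.05 × 0.95/4000) = 0.3 percentage points.

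**Test.** Averaged PHDD = b0 + b1·arm + b2·split + b3·arm×split + baseline + site, testing b3 = 0. This is a complete-data stand-in for the SAP 9.4.1 model.

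**Reading rules.** Let D(x) be the oxytocin curve minus the placebo curve at moderator value x. The SAP states no rule, so four plausible ones were tried: where |D| is largest; where D = 0 (the curves cross); where D is steepest; and the cut giving the largest difference between mean D below and above it.

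**Rejection at p < 0.05 with no true moderation:**

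| Cut | Adjusted, 19 settings | Adjusted, repeat | Unadjusted, d = 0 |
|---|---|---|---|
| None (continuous score) | 4.4-5.6% | 4.5-5.5% | not run |
| Median, fixed in advance | 4.7-5.6% | 4.5-5.5% | 5.2-5.4% |
| Largest gap | 3.7-5.8% | not run | not run |
| Crossing | 4.9-5.8% (d = 0.6); 5.8-9.0% (d = 0) | 5.5-7.0% | 6.4-10.0% |
| Steepest point | 6.4-8.5% | 7.1-7.6% | not run |
| Largest change | 7.3-10.7% | 9.5-10.0% | 9.8-14.2% |

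Where the curves do not cross, the 19-setting runs use the median; the other two columns count closest approach as a crossing. The last column omits baseline and site, uses span 2/3, lets a subgroup-by-arm cell fall to 10%, 20% or 30% of the arm, and has 1200 runs per setting. It is further from the planned model and is shown for sensitivity.

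**Correction implied.** At correlation 0.5 and d = 0.6, holding a true 5% would need p < 0.024-0.027 at the largest-change cut and p < 0.034-0.035 at the steepest point.

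**Apparent effect.** With no moderation, the mean absolute difference between the two subgroup effects is 0.39-0.40 SD at the largest-change cut, against 0.30-0.31 SD at a median split. Part of this comes from less even subgroups.

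**If the split is display only.** The interaction p-value is unaffected. What remains is the p-values within each split. In the unadjusted runs the chance that at least one of the two is below 0.05 was 9.4-11.1% at the median (two independent tests would give 1 − 0.95² = 9.8%), 10.7-11.8% at the crossing and 14.8-18.7% at the largest change.

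**The case against.** **The split may be for display only.** SAP 9.11 names the interaction first and dichotomizes afterwards as an aid to interpretation. Table 117 does not settle the matter, because its own moderator is a yes/no item and one degree of freedom fits either form. This stands as a real ambiguity. The flat statement in protocol 11.4.7, and the absence of any named continuous test, lean towards a test on the split but do not prove it. Even on the display reading, the shell puts subgroup p-values at the cut.

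**The cut is constrained.** The subgroup-size requirement does limit the choice, and the 25th-75th percentile limit in the main runs is one reading of it. It is not a reading rule, and inflation remains within it for some rules.

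**The size is not fixed by the documents.** This also stands. Every reading rule above is an assumption. One gives no material inflation, and another gives little at the design effect. A reader might infer that the false-positive rate doubles, or look to an outright smallest-p search, which gave 21-40% in the unadjusted runs. The SAP describes no such search, and doubling is the top of the range.

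**Wider readings to avoid.**
- A reader might see a contradiction between "conducting moderator analyses using the total score" in protocol 11.4.7 and the SAP's addition of subscales. Protocol 11.1 lets the SAP add exploratory analyses, so no protocol change is required.
- A reader might assume the Hyperkatifeia cut will be the scale's first published result. The documents say only that the scale is first assessed here.
- The fallback should not be assumed for every scale. SAP 9.12 notes proposed cutpoints for IDS-30, and the documents do not show whether the other scales have accepted cutoffs.

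**Conclusion.** The concern holds as a minor one. For at least the Hyperkatifeia score, the plan allows an outcome-derived cut with uncorrected p-values on the same data. An interaction test on the split then has a false-positive rate of about 5% to about 10% at nominal 5%, depending on a choice left to whoever reads the curves. The range assumes 88 complete subjects, adjustment for baseline and site, cuts in the middle half of the moderator and the four reading rules tried. Its direction needs less: the inputs named in SAP 9.11 are enough to show that the cut is not independent of the test.

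The consequence is limited. The analyses are labelled exploratory, protocol 11.4.11 calls the trial a pilot, and SAP 9.1 attaches statistical significance only to primary and secondary endpoints. The primary comparison is unaffected. Multiplicity across the many moderators is a separate matter.

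**What to change.** Change SAP 9.11 only:

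1. Where no published cutoff exists, fix the cut before unblinding from the blinded pooled baseline distribution of the moderator, for example the median.
2. Keep LOESS plots as description, including as a check on the shape of any interaction. Give no p-value at a LOESS-derived cut.
3. State whether the interaction in the amended SAP 9.4.1 model uses the continuous score or the split.

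No protocol amendment or new data are needed, and the two-group display stays.

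The cost is that a pre-fixed cut may miss the true threshold. With an assumed interaction of 0.6 SD per SD, d = 0.6 and baseline correlation 0.5, power for a step at the 70th percentile was 49-50% for a median split, against 63-68% for LOESS change cuts held to a true 5%.

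For item 3, the continuous interaction is reasonable but not always better:

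| True shape | Continuous | Median split |
|---|---|---|
| Linear | 86-87% | 65-67% |
| Step at median | 66-68% | 79-81% |
| Step at 70th percentile | 61% | 49-50% |
| U-shape | 11-13% | 5% |

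The assumed interaction is large. At 0.3 SD per SD and linear moderation, power falls to about 36% and 25%. Either form is acceptable if stated in advance.

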9.12 Ad hoc Analyses

Ad hoc analyses may be performed on the Hyperkatifeia Scale as a planned part of exploring the utility of this scale including total scores, subscales, and individual items. Ad hoc analyses utilizing Hyperkatifeia Scale scores may include: 1) identification of baseline subsets and relationship to alcohol-related outcomes; 2) conducting mediator analyses; 3) factor analysis to better understand the underlying dimensions of hyperkatifeia; 4) validity of the Hyperkatifeia Scale by comparing to other measures (e.g., POMS and PROMIS scales or subscale scores); and 5) and further evaluation of the scales as endpoints to assess treatment efficacy. The data from this study could be used for meta-analyses with results of other studies to expand data availability for the proposed ad hoc analyses.

Ad hoc analyses may also be performed on the Drinking Goal questionnaire as a predictor and moderator of alcohol-related outcomes. Cutpoints for IDS-30 reward and relief drinkers have been proposed for high and low levels of each, creating 4 categories (Votaw et al, 2022). These categories will be related to drinking outcomes if there are sufficient sample sizes within each category.

